10.3 Scheduled Follow-up Visit Windows

After receiving notice of successful implantation/device application, Medtronic will provide the target dates and windows for each visit to the study site if applicable. Should a subject miss a visit or the visit fall outside the pre-specified window, a study deviation must be reported and the original follow-up schedule maintained for subsequent visits.

Medtronic Business Restricted

China CIED 3.0T MRI Performance Study Clinical Investigation Plan

MDT23009

Version 2.0

Page 23 of 60

Medtronic

Data analyses include follow-up visits, regardless of whether the visit occurs within the window. Therefore, a late visit is preferred over a missed visit but must be accompanied by a deviation report. Follow-up visit windows are listed in Table 5 and are based on days post MRI scan.

Table 5: Scheduled follow-up visit window

Study Follow-up Visit	Window(Calculated days post-MRI visit)		
	Window Start (days post-MRI)	Target (days post- MRI)	Window End (days post-MRI)
MRI visit*	-	-	-
1 month post MRI	30	30	56

*highly recommend completing the MRI scan within 30 days after baseline visit

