	
 • foetal distress, foetal death or a congenital abnormality or birth defect including physical or mental impairment. 
Note: Planned hospitalization for a pre-existing condition, or a procedure required by the CIP, without serious deterioration in health, is not considered a SAE. (ISO 14155:2020, section 3.45)

Complication	
An adverse event that includes the following is considered a complication:
 
 • Results in death, • Involves any termination of significant device function, or • Requires an invasive intervention 
Non-invasive (21 CFR 812.3(k)): when applied to a diagnostic device or procedure, means one that does not by design or intention: Penetrate or pierce the skin or mucous membranes of the body, the ocular cavity, or the urethra, or enter the ear beyond the external auditory canal, the nose beyond the nares, the mouth beyond the pharynx, the anal canal beyond the rectum, or the vagina beyond the cervical os
 
Note: Only system or procedure related AEs will be classified for complication/observation

Observation	
Any adverse event that is not a complication.
 
Note: Only system or procedure related AEs will be classified for complication/observation

Other	
Unavoidable Adverse Event Related to the MRI Procedure	
An Adverse Event inherent to a MRI procedure that is expected to occur in all subjects for a projected duration according to the Investigator's opinion, including, but not limited to:

Medtronic Business Restricted

China CIED 3.0T MRI Performance Study Clinical Investigation Plan

MDT23009

Version 2.0

Page 37 of 60

Medtronic

Definition	Description	
	Event Description	Timeframe (hours) from the MRI Procedure
	Claustrophobia	During MRI
	Mild diaphoresis	During and < 1 hour post-MRI
	Hearing impairment	<24 hours
	Mild lightheadedness	<30 minutes
	Sensation of bodily warmth	<1 hour
	Body stiffness related to immobility	<48 hours
	UAE listed in the above table need not be reported unless the adverse event worsens or is present outside the stated timeframe post-implant.	
Hospitalization	A therapeutic inpatient hospitalization (excludes observation unit, emergency room and outpatient visits) lasting greater than or equal to 24 hours, or overnight.	

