14.3 Secondary Objective(s) Atrial and Ventricular Pacing Capture Thresholds

To characterize changes in atrial and ventricular pacing capture thresholds (APCT and VPCT) from pre-MRI to 1-month post-MRI scan

Hypothesis

There is no hypothesis for this objective.

Endpoint Definition

PCTs to be evaluated include:

- APCT of atrial lead for subjects with an IPG device
- APCT of atrial lead and VPCT of right ventricular (RV) lead for subjects with an ICD device
- APCT of atrial lead and VPCTs of right ventricular (RV) and left ventricular (LV) leads for those with a CRT-D device.

Medtronic Business Restricted

China CIED 3.0T MRI Performance Study Clinical Investigation Plan

MDT23009

Version 2.0

Page 44 of 60

Medtronic

PCTs of each subject will be measured prior to the 3.0T MRI scan and at the one month post-MRI. Change in PCT is defined as PCT measured at one month post-MRI subtracts that measured prior to a 3.0T MRI scan. Proportion of subjects with an increase less than or equal to 0.5V in APCT or VPCTs from pre-MRI to one-month post-MRI will also be used to characterize the efficacy performance of SureScan with respect to PCTs.

If the 1-month post-MRI APCT or VPCT is missing, the PCT measured immediately post-MRI will be used instead.

Performance Requirements

There are no performance requirements.

Rationale for Performance Criteria

The 0.5V threshold for the increase in a PCT from pre-MRI to one-month post-MRI is consistent with what have used in the FDA approved pre-market MRI studies such as EnRhythm MRI, Advisa MRI, and Evera MRI.

Analysis Methods

The change in PCT is the PCT measured at one month post-MRI subtracts that measured prior to a 3.0T MRI scan. Descriptive statistics such as mean and standard deviation will be provided for changes in APCT and VPCTs, respectively.

In addition, the percentage of subjects with an increase less than or equal to 0.5V from pre- to one month post-MRI in APCT and VPCTs will be determined.

Determination of Patients/Data for Analysis

To be included in the analysis, all of the following must be met:

- The subject must undergo a 3.0T MRI scan.
- The subject must have valid PCT measurements pre and post-MRI (see paragraph below for definitions).
- The (atrial, right or left ventricular) lead is not dislodged within 6 weeks prior to MRI scan.

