- The (atrial, right or left ventricular) lead has not been replaced or repositioned within 6 weeks prior to MRI scan or between MRI scan and the one-month post-MRI visit.
- The VPCTs of RV at the pre-MRI must be $\leq 2.0V$. This is because subjects with a higher VPCT cannot have an MRI per CIP

To be a valid PCT measurement, the pulse width must be set to 0.4ms and a printed pacing capture threshold testing strip must be available to confirm the pulse width and capture threshold reported.

The pre-MRI period value will be the pre-MRI period PCT measurement. For the post-MRI period PCT value, the PCT value on the one-month post-MRI period CRF will be used. If that does not exist or is not valid, the PCT measured immediately post-MRI will be used instead.

Medtronic Business Restricted

[figure not shown]
China CIED 3.0T MRI Performance Study Clinical Investigation Plan

MDT23009

Version 2.0

Page 45 of 60

Medtronic

Medtronic Business Restricted

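### Minor: two cause-blind rules let a lead that fails after the scan drop out of the descriptive ≤ 0.5 V percentage or, depending on how non-capture is recorded, count as a success in it

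*Combined protocol and SAP*

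**What the plan says.** CIP 14.3 describes the change in atrial and ventricular pacing capture thresholds from before the scan to one month after it. It gives the mean and SD of the change, and the percentage of subjects whose threshold rose by no more than 0.5 V. That percentage "will also be used to characterize the efficacy performance of SureScan with respect to PCTs". There is no hypothesis, and "There are no performance requirements".

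The rules that decide which leads enter are the same in CIP 14.3 and SAP 7.9.2.6:

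- **Revision.** A lead is left out if it was replaced or repositioned in the six weeks before the scan "or between MRI scan and the one-month post-MRI visit". No exception is made for cause.
- **Validity.** For a threshold to be valid, "the pulse width must be set to 0.4ms and a printed pacing capture threshold testing strip must be available to confirm" the result.
- **Substitution.** For a one-month value that fails this or is absent: "If that does not exist or is not valid, the PCT measured immediately post-MRI will be used instead". The reason plays no part.
- **2.0 V limit.** RV leads with a pre-scan threshold above 2.0 V are left out, on the ground that the CIP bars such subjects from the scan. Appendix A states that limit only for pacemaker-dependent patients.

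The documents differ on which chambers are analysed. The list in CIP 14.3 and SAP 7.9.2.2 gives only "APCT of atrial lead for subjects with an IPG device", RV for ICD and CRT-D, and LV for CRT-D. The synopsis, CIP 5.1.2 and SAP 4.1.2 name the ventricular threshold without excluding pacemaker subjects.

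**The concern.** The percentage is the plan's yes/no measure of whether pacing thresholds survive a 3.0T scan. CIP 11.1 lists electrode heating with loss of capture, and lead dislodgement, among the risks. A lead with that outcome is likely to be revised before the one-month visit or to have no threshold obtainable at 0.4 ms. The first route removes it from the percentage. The second may let a scan-day value stand in for it, and that value was taken before a delayed failure could show.

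Excluding a revised lead is sensible for the mean, because the before and after values no longer describe the same lead position. A percentage does not need a measured change to classify a lead that has plainly failed. No sensitivity analysis covers this: the SAP's tipping point analysis is for the primary endpoint only. At stake is the accuracy of one reported efficacy figure.

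**Working it through.** **The plan's own figure.** None is given for this objective. The nearest is the primary sample size of 54, which reproduces. Rejecting at 53 or more of 54 gives alpha = 0.9^54 + 54 × 0.1 × 0.9^53 = 0.0237 and power = 0.995^54 + 54 × 0.005 × 0.995^53 = 0.9699. Enrolment is 54 / 0.85 = 63.5, so 64. None of this changes below.

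**What happens to each kind of lead under the written rules**

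| Lead after the scan | Treatment as written | Status in the ≤ 0.5 V percentage |
|---|---|---|
| Valid one-month value, rise > 0.5 V | Kept | Failure (correct) |
| Revised for threshold rise or capture loss before the visit | Excluded | Absent |
| No capture at 0.4 ms, recorded as missing or invalid; scan-day rise ≤ 0.5 V | Scan-day value used | Success |
| One-month value missing; scan-day rise > 0.5 V | Scan-day value used | Failure |

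**Size.** Let n be the leads in one chamber and s the leads that truly meet ≤ 0.5 V. Counting failed leads as failures gives s/n. With one failed lead hidden:

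- excluded: s/(n − 1), an increase of s/(n(n − 1)), which is at most 1/n because s ≤ n − 1;
- substituted as a success: (s + 1)/n, an increase of 1/n.

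The documents give no lead counts, so n is assumed. The value 54 applies to RV leads if every evaluable subject contributes one, as the synopsis, CIP 5.1.2 and SAP 4.1.2 read. Smaller values fit the narrower list in CIP 14.3, or the LV lead.

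| n | One hidden failure, no other rise: true → shown | One counted rise plus one hidden failure: true → excluded / substituted |
|---|---|---|
| 54 | 53/54 = 98.1% → 100% | 52/54 = 96.3% → 52/53 = 98.1% / 53/54 = 98.1% |
| 40 | 39/40 = 97.5% → 100% | 38/40 = 95.0% → 38/39 = 97.4% / 39/40 = 97.5% |
| 20 | 19/20 = 95.0% → 100% | 18/20 = 90.0% → 18/19 = 94.7% / 19/20 = 95.0% |
| 10 | 9/10 = 90.0% → 100% | 8/10 = 80.0% → 8/9 = 88.9% / 9/10 = 90.0% |

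**Direction.** Relative to counting failures, both rules leave the figure unchanged or raise it. Relative to dropping leads with no one-month value, substitution can lower it: with 20 leads, keeping one scan-day rise above 0.5 V gives 19/20 = 95.0%, against 19/19 = 100% if that lead were dropped.

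**How often.** At the plan's 0.995 event-free rate, 54 subjects give 54 × 0.005 = 0.27 expected primary events and a chance of at least one of 1 − 0.995^54 = 0.237. This is a rough scale only. It covers every kind of primary event, and omits revisions not judged MRI-related or made after day 30.

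**The case against.** **It is a choice of estimand.** The objective is to describe changes in threshold, and a repositioned lead has no comparable change. Failures belong to the primary endpoint. This stands for the mean and SD. It is weaker for a percentage offered as evidence of efficacy, where the exclusion removes leads because of the outcome being summarised.

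**The substitution route is hypothetical.** The documents do not say how non-capture is recorded. A strip run at 0.4 ms that shows no capture is not declared invalid, and CIP 10.8 requires threshold testing at one month. This stands: the second route is conditional. The first route does not depend on it.

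**Failures are reported elsewhere.** The complication definition in CIP Table 7 has no chamber limit. It includes an event that "Requires an invasive intervention" and one that ends a significant device function, so an MRI-related revision of any lead to day 30 is a primary event. Adverse events are listed individually (SAP 7.10), and SAP 7.4 and 7.7 tabulate the available thresholds. This stands as disclosure, and it keeps the point minor. None of it corrects the percentage.

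**The 2.0 V wording is a different matter.** Agreed. Appendix A also invokes the product MRI technical manual, which is not in the documents and may be stricter. If it is, the criterion drops nobody.

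**Conclusion.** The point holds as a minor one, confined to a descriptive secondary summary. The revision exclusion removes failed leads from the ≤ 0.5 V percentage whatever the cause. The substitution rule can turn a failed lead into a success if non-capture is recorded as missing or invalid. Each hidden lead moves the figure by at most 1/n: 1.9 points at 54 leads and 10 points at 10. These sizes rest on assumed lead counts and on the other leads behaving as tabulated.

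A reader might infer more than the documents support:

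- **That the safety conclusion is affected.** It is not. The primary analysis keeps subjects with MRI-related events and does not use this percentage.
- **That every failing lead is hidden.** A valid high one-month value is kept and counted.
- **That denominators must be small.** The narrower list in CIP 14.3 suggests so for RV leads. The synopsis, CIP 5.1.2 and SAP 4.1.2 do not, and CIP 7.1.1 gives every configuration an RV lead.
- **That a late revision appears only among adverse events.** In CIP 10.3, "Follow-up visit windows are listed in Table 5 and are based on days post MRI scan", and the one-month visit may fall on days 30 to 56. A revision after day 30 but before that visit is outside both the percentage and the 30-day primary endpoint. The subject's available thresholds still enter the SAP 7.4 and 7.7 summaries.
- **That the 2.0 V criterion biases the result.** It conflicts in wording with Appendix A, but whether it drops anyone, and in which direction that would act, is unknown.

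**What to change.** In the ≤ 0.5 V percentage only, score a lead as not meeting the criterion if it was revised for threshold rise or loss of capture, or is documented as not capturing at 0.4 ms at one month. Take the cause from the adverse event forms and the medical advisor review already planned. Leads revised for other reasons stay excluded. Keep mean and SD on leads with valid paired values. Report the percentage with and without the scan-day substitution, and give the number of excluded and substituted leads with the reason for each.

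State in the SAP how non-capture at 0.4 ms is recorded, and settle whether RV thresholds of pacemaker subjects are analysed.

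Separately, reconcile the 2.0 V criterion with Appendix A. If non-dependent subjects above 2.0 V may be scanned, keep their valid paired values. If the product manual bars them, correct Appendix A and leave the criterion.

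The cost is wording and minor programming. Sample size, alpha and the primary analysis are unchanged. Under CIP 14.1 an amendment is needed only if a principal feature changes; otherwise a justified note in the study report suffices. The scoring uses data already planned, although sites may need an instruction if the form has no place for non-capture. The downside is that the reported percentage may be slightly lower.

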14.5 Sample Size Determination

Sample Size

The sample size estimation is based on the following assumptions:

- α (the type I error rate) = 0.025
- power $(1 - \beta)$ = 90%
- P_0 (proportion under null hypothesis) = 0.90
- P_1 (assumed true proportion) = 0.995. Rationale for 0.995: There have been 0 MRI-related events in previous MRI studies (EnRhythm MRI, Advisa MRI and 5076 MRI for IPG devices and Evera MRI for ICD devices).

The sample size calculation is performed using the inequality tests for one proportion with a one-sided, one-sample proportion exact test in PASS (2008). Under the above assumptions, the minimum required sample size is 54 subjects to undergo a 3.0T MRI scan and be followed for at least 1 month post MRI procedure.

Attrition from enrollment to completion of an MRI scan and being following for one month post MRI ranges from 12% to 18% in historical MRI studies (Table 11). Assuming an attrition rate of 15%, a total enrollment of 64 subjects is needed in the China 3.0T MRI study. If the actual attrition rate exceeds 15%, further evaluation may be considered.

15. Ethics

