5.1.2 Secondary Objective

To characterize changes in atrial and ventricular pacing capture thresholds (APCT and VPCT) from pre-MRI to one month post-MRI scan

Endpoint Definition

The effectiveness of the Surescan MRI CIED device will be measured by the following parameters

[figure not shown]
- Atrial pacing capture threshold (if applicable)
- Ventricular pacing capture threshold (both right and left ventricular lead if applicable)

These parameters will be measured pre-MRI scan, immediately post MRI scan and 1-month post MRI scan.

Rationale

Medtronic Business Restricted

While PCT and sensing amplitude changes will contribute to the effectiveness objective, the increased PCT will affect the pacing effectiveness and the lifetime of device.

6. Study Design

The China CIED 3.0T MRI Performance study is a prospective, non-blinded, multi-site, interventional post-market study. The study is expected to be conducted at mainland China. Participating devices are expected to include single/dual chamber transvenous IPG, single/dual chamber ICD and CRTD.

The number of enrolled subjects in the study is 64 considering the attrition. To ensure a reasonable distribution of experience and minimize site bias in study results, the maximum number of subjects enrolled at each site will be capped at 30% of total subjects enrolled. All subjects will have required follow-up visits at baseline, MRI visit, 1-month post-MRI. The MRI scans will occur at the MRI visit. The MRI scan region will be determined by investigator according to the subject's clinical condition.

Ethics Committee approval of the study CIP and informed consent must be obtained prior to the site enrolling patients. Subject medical history will be verified to ensure patients meet all the inclusion and none of the exclusion criteria.

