16.6 CIP Amendments

Any revisions or amendments to the CIP or IC document, along with a statement of justification for the changes, will be submitted to governing ECs, according to applicable regulations. All amendments to the CIP shall be agreed upon between Medtronic and the principal investigator(s), or the coordinating investigator. Approval by regulatory agencies and ECs (where applicable) must be obtained prior to implementing a CIP revision at the study site.

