P1 (Alternative Proportion):

Test
H1 (Alternative Hypothesis):
Test Type:
N (Population Size):

TEST TYPE:
Specify which type of test will be used in all searching and reporting.

Note that 'C.C.' is short for 'Continuity Correction.' This refers to the adding or subtracting $1/(2n)$ to (or from) the numerator of the z-value to bring the normal approximation closer to the binomial distribution.

Template Id:
Reset Guide Me

Power Analysis of One Proportion

Page/Date/Time 1 10/4/2024 4:13:55 PM

Numeric Results for testing $H_0: P = P_0$ versus $H_1: P > P_0$

Test Statistic: Exact Test

Power	N	Proportion	Proportion	Target Alpha	Actual Alpha	Reject H_0	
		Given H_0	Given H_1			Beta	If $R \geq$ This
0.9699	54	0.9000	0.9950	0.0250	0.0237	0.0301	53

References

Fleiss, J. L., Levin, B., Paik, M.C. 2003. Statistical Methods for Rates and Proportions. Third Edition. John Wiley & Sons. New York.
Lachin, John M. 2000. Biostatistical Methods. John Wiley & Sons. New York.
Zar, Jerrold H. 1984. Biostatistical Analysis (Second Edition). Prentice-Hall. Englewood Cliffs, New Jersey.

Report Definitions

Power is the probability of rejecting a false null hypothesis. It should be close to one.
N is the size of the sample drawn from the population. To conserve resources, it should be small.
Alpha is the probability of rejecting a true null hypothesis. It should be small.
Beta is the probability of accepting a false null hypothesis. It should be small.
 P_0 is the value of the population proportion under the null hypothesis.
 P_1 is the value of the population proportion under the alternative hypothesis.

Summary Statements

A sample size of 54 achieves 97% power to detect a difference ($P_1 - P_0$) of 0.0950 using a one-sided binomial test. The target significance level is 0.0250. The actual significance level achieved by this test is 0.0237. These results assume that the population proportion under the null hypothesis is 0.9000.

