7.3 Poolability

This study plans to enroll up to 64 subjects in China. Poolability analysis will not be performed due to small sample size, single geographical region, and few sites.

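### Is an enrolment of 64 too small, given that the plan's own attrition range runs to 18%?

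*Combined protocol and SAP*

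**What the plan says.** CIP 14.5, repeated in SAP 6, sizes the study for a one-sided exact binomial test with α = 0.025, a null event-free rate of 0.90, an assumed true rate of 0.995 and target power of 90%. It concludes that "the minimum required sample size is 54 subjects". The PASS output in SAP 6 gives the operating characteristics at that size: "A sample size of 54 achieves 97% power to detect a difference", actual α 0.0237, rejection if at least 53 are event-free.

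On losses, the section reports that attrition from enrolment to the end of one-month follow-up "ranges from 12% to 18% in historical MRI studies". It continues: "Assuming an attrition rate of 15%, a total enrollment of 64 subjects is needed in the China 3.0T MRI study". For a worse outcome it offers one sentence: "If the actual attrition rate exceeds 15%, further evaluation may be considered".

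Elsewhere the enrolment figure reads as fixed. CIP 6 and SAP 5 state: "The number of enrolled subjects in the study is 64 considering the attrition". SAP 7.3 words it as a ceiling: "This study plans to enroll up to 64 subjects in China". Any increase would go through CIP 16.6: "Approval by regulatory agencies and ECs (where applicable) must be obtained prior to implementing a CIP revision at the study site". Under CIP 14.2 and SAP 7.9.1.5, subjects lost before the one-month visit leave the primary denominator unless they have already had an MRI-related event.

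**The concern.** At 15% attrition, 64 enrolled leaves an expected 54.4 evaluable against a minimum of 54, a cushion of less than half a subject. In most designs a shortfall of one or two subjects costs almost nothing. Here the exact test is discrete, and 54 is the smallest number at which one event can be tolerated. Falling to 53 removes that allowance and about 20 points of power. The 11th loss is enough to cause it, and 11/64 = 17.2% lies inside the range the plan itself cites.

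The sentence on higher attrition looks weak as a safeguard. It is optional, names no action, and sits beside an enrolment figure that can be raised only by amendment. Attrition counts from consent and includes subjects who exit on failing the pre-MRI check (CIP 10.7). The final rate is known only after recruitment has closed. What would be at stake is a safe system failing the study's only hypothesis test, with a probability of 23% at 53 evaluable instead of 3% at 54.

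**Working it through.** **Inputs (CIP 14.5, SAP 6).** P0 = 0.90; P1 = 0.995; one-sided α = 0.025; 54 evaluable; 64 enrolled; attrition 12% to 18%, planning value 15%. Success requires a one-sided 97.5% Clopper-Pearson lower bound above 90% (CIP 14.2).

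**1. The plan's own figures.**
- Power at 54 with at most one event: 0.995^54 + 54 × 0.005 × 0.995^53 = 0.7629 + 0.2070 = 0.9699.
- Actual α: 0.90^54 + 54 × 0.10 × 0.90^53 = 0.0034 + 0.0203 = 0.0237.
- Enrolment: 54/0.85 = 63.5, rounded up to 64. Back-check: 64 × 0.85 = 54.4.

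All agree with the documents.

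**2. The step at 54.** Lower bounds, and power at 0.995:

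| Evaluable | Bound, 0 events | Bound, 1 event | Events allowed | Power | Type I error |
|---|---|---|---|---|---|
| 36 | 90.26% | 85.47% | 0 | 83.5% | 0.0225 |
| 52 | 93.15% | 89.74% | 0 | 77.1% | 0.0042 |
| 53 | 93.28% | 89.93% | 0 | 76.7% | 0.0038 |
| 54 | 93.40% | 90.11% | 1 | 97.0% | 0.0237 |
| 64 | 94.40% | 91.60% | 1 | 95.9% | 0.0096 |

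From 36 to 53 evaluable, no event is allowed and power falls from 83.5% to 76.7%. Below 36 the test cannot succeed: 0.90^35 = 0.02503, just above 0.025. Type I error is under 0.025 at every size.

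**3. Losses that 64 can absorb.** 64 − 54 = 10 losses, or 15.6%. The 11th (17.2%) leaves 53. Expected evaluable numbers are 64 × 0.88 = 56.3, 64 × 0.85 = 54.4 and 64 × 0.82 = 52.5.

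**4. Power before the evaluable number is known.** The 77% holds only if the number comes out at about 52 or 53. If each of the 64 is lost independently with the stated probability (an assumption that the plan does not make), then weighting the power at each evaluable number by its binomial probability gives:

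| Attrition | Chance of fewer than 54 | Average power, P1 = 0.995 |
|---|---|---|
| 12% | 14.0% | 93.9% |
| 15% | 36.3% | 89.7% |
| 18% | 61.8% | 85.0% |

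So average power is about on target at the planning value and about 5 points short at the upper end.

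**5. Dependence on the assumed true rate.**

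| P1 | Power at 54 | Power at 53 | Power at 52 | Average, 64 enrolled, 18% attrition |
|---|---|---|---|---|
| 0.99 | 89.8% | 58.7% | 59.3% | 71.3% |
| 0.995 | 97.0% | 76.7% | 77.1% | 85.0% |
| 0.998 | 99.5% | 89.9% | 90.1% | 93.8% |

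**6. What more subjects would buy.** By the plan's own method, 54/0.82 = 65.9, so 66 at 18% attrition. Average power at 18% (P1 = 0.995) is then 88.9%; with 67 it is 90.6%. Even with 67, the chance of ending below 54 at 18% attrition is 31.4%.

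**The case for a change.** The strongest case for a change is that the minimum is an unusually sharp threshold, the sponsor's own range crosses it, and the remedy is small. Three more subjects take about 10 days at the planned pace (64 in 7 months is 9.1 a month, and 3/9.1 = 0.33 month). The study is not blinded, so adding subjects later under an undefined evaluation could look as if event counts drove it. A fixed larger number, or a replacement rule, would settle both points in advance.

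The description of the threshold stands, and so does the vagueness of the contingency sentence. The need for a change does not.

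- **Choice of attrition rate.** The midpoint of a cited range is an ordinary planning value. CIP Table 11 is not visible in the text reviewed, so the weight that 18% deserves cannot be judged.
- **Limits on losses.** Subjects are screened before they sign consent (CIP 9.2), baseline and scan may share a day (CIP 10.6), and late visits still count (CIP 10.3).
- **Warning time.** The 15% mark is passed at the 10th loss, while 54 can still be evaluable. Many losses will show during enrolment: the scan is recommended within 30 days of baseline and the follow-up window closes at day 56. The amendment route in CIP 16.6 is open.
- **A larger fixed number** moves the threshold without removing it. With 67 enrolled it returns at the 14th loss (20.9%).
- **Replacement until 54 are in the primary denominator** has a difficulty of its own. That denominator takes in a non-completer only if an MRI-related event has occurred, so the count cannot be formed without reference to events.

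**Conclusion.** No change is needed. The sizing is correct at the attrition it assumes, the PASS result reproduces, and the plan misses no power or sample size that it states. What remains is a thin margin: from the 11th loss on, no event is tolerated and power at 0.995 is about 77%. Averaged over binomial dropout, power is about 90% at 15% attrition and 85% at 18%. Those averages assume independent losses and a true rate of 0.995. At 0.998 the 18% figure is 93.8%; at 0.99 it is 71.3%.

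The exposure is a higher chance of an inconclusive result, carried mainly by the sponsor in a post-market study of approved devices. It cannot make an unsafe system look safe, because the exact test holds its level at any evaluable number. Enrolling 66 or 67 would be a reasonable preference at the design stage, but it corrects nothing. The open contingency sentence is a gap that can be filled without altering any result: if fewer than 54 are evaluable, the same test is run, and the report says that no event was allowed and that power at 0.995 was about 77% to 83%.
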